11.2 Secondary Objectives:

- 1) To compare the primary endpoint by race (African American [AA] vs Other).
- 2) To compare the rates of each of 2 types of response by treatment arm:
 - a) Measurable disease response; and
 - b) PSA response.
- 3) To compare each of 7 time-to-event endpoints by treatment arm:
 - a) Duration of overall response (RD);
 - b) Duration of stable disease (SDD);
 - c) Time to treatment failure (TTF);
 - d) time-to-progression (TTP);
 - e) TTP in patients with bone metastases;
 - f) progression-free survival (PFS); and
 - g) Overall survival (OS).
- 4) To compare the rates of each type of toxicity by treatment arm.
- 5) To compare the incidence rate of skeletal related events (SRE), and the time until SRE, separately by treatment arm.
- 6) To compare the rates of CTC response by treatment arm..
- 7) To explore the molecular mechanisms within the androgen receptor pathway by determining the levels of CXCR4 and TMPRSS2-ERG expression, androgen metabolism enzymes, androgen receptor variants, and length of CAG repeats within the androgen receptor gene, and to associate them with the primary endpoint.

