11.3 Endpoints

11.3.1 For the primary objective, the binary endpoint will be the achievement of PSA remission at month 7 (yes or no). This endpoint is described in the Study Schema and in Section 8.1.

11.3.2 For secondary objective (1), the primary endpoint is described in the Study Schema and in Section 8.1. The two race groups to be compared are AA vs Other, as described in the Study Schema.

11.3.3 For secondary objective (2), the endpoints will be the achievement of:
a) measurable disease response (yes or no), (defined in Sections 8.0 and 8.9); and
b) PSA response (as defined in Section 8.2).

11.3.4 For secondary objective (3), the endpoints will be the length of censored:
a) duration of overall response (RD), as defined in Section 8.3;
b) duration of stable disease (SDD), as defined in Section 8.4;
c) time to treatment failure (TTF), as defined in Section 8.5;
h) time-to-progression (TTP), as defined in Section 8.6;
i) TTP in patients with bone metastases, as defined in Section 8.7;
j) progression-free survival (PFS), as defined in Section 8.8; and
k) overall survival (OS), as defined in Section 8.9.

11.3.5 For secondary objective (4), the endpoints will be the occurrence rate of each specific type of toxicity observed (defined in Section 6.0) and treatment arm (A or B, defined in Study Schema, Section 5.3, and Section 11.1).

11.3.7 For secondary objective (5), the endpoints will be the occurrence rate of SRE (defined in Section 8.12), the distribution of time until SRE, and treatment arm (A or B). Follow-up for SRE will continue until SRE, PSA progression, or death, whichever occurs first.

11.3.8 For secondary objective (6), the endpoints will be the occurrence rate of CTC response (defined in Section 8.13), and treatment arm (A or B).

11.3.9 For secondary objective (7), the endpoints will be the expression levels of the selected genes or enzymes stated in Section 11.2, length of CAG repeats, and the primary endpoint of PSA remission at month 7 (yes or no). The correlates are defined and described in Section 10.0. The expression level of those biomarkers will be determined in both pre- and posttreatment prostate tumor tissues, and in post-treatment bone biopsy samples

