11.6 Analysis

11.6.1 For the primary objective, the binary endpoint (PSA remission at month 7, yes/no) will be summarized with its point estimate (an occurrence rate), and 2-sided Wilson type 95% confidence interval (CI). This analysis will be performed two ways: a) for all randomized patients (the intention to treat subset); and b) for all r-e patients (the per protocol subset). PSA response rates will be compared by treatment arm in a stratified logistic regression model, with stratification by race (AA, Other) and bone pain (yes, no).

11.6.2 All binary endpoints in secondary objectives 1-2 and 4-7, will be summarized with point estimates (occurrence rates), and 2-sided Wilson type 95% CIs. The analysis of toxicity rates will be performed using only the toxicity-evaluable (t-e) patients (defined in Section 8.11).

11.6.3 For secondary objective 4, the grade of each type of toxicity (an ordinal categorical variable) will be summarized with 1-way frequency distributions. A similar descriptive analysis will be performed for any correlatives in secondary objective 7 to be assayed by IHC, resulting in ordinal categorical variables (intensity levels of 0, 1+, 2+, or 3+).

Dichotomized versions (e.g., the occurrence rate of Grade 3-4 neutropenia) will be summarized as described in Section 11.6.2. A similar descriptive analysis will be performed for the presence/absence of any correlatives in secondary objective 7 to be assayed by IHC, with presence defined as intensity level of 1+ through 3+.

For any correlatives in secondary objective 7 that are assayed in both pre- and post-treatment prostate tumor tissues, the change in IHC expression level will be described using a 2-way frequency distribution. If the effective sample size appears to be sufficient relative to the size of the 2-way table, the association of these paired variables can be tested with the exact version of McNemar's test.

11.6.4 All censored time-to-event distributions for secondary objectives 3 and 5 will be estimated with standard Kaplan-Meier (K-M) methodology. Point and CI estimates of the median and various time point-specific rates will be derived from the K-M life table. The censored K-M distributions will be compared with the log-rank test, stratified by race (AA, Other) and bone pain (yes, no).

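### Secondary objective 1 is to compare PSA remission between African American and Other patients, but the analysis section gives only separate rates with Wilson intervals and no contrast; four by-arm binary endpoints share the gap

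*Combined protocol and SAP*

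**What the plan says.** **Objectives and endpoints.** Secondary objective 1 in Section 11.2 reads "To compare the primary endpoint by race (African American [AA] vs Other", and 11.3.2 adds "The two race groups to be compared are AA vs Other, as described in the Study Schema". Four other secondary objectives in 11.2 with binary endpoints use the same verb, by treatment arm:

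- objective 2: "To compare the rates of each of 2 types of response by treatment arm" (2a is measurable-disease response, 2b is PSA response);
- objective 4: "To compare the rates of each type of toxicity by treatment arm";
- objective 5: "To compare the incidence rate of skeletal related events (SRE), and the time until SRE, separately by treatment arm";
- objective 6: "To compare the rates of CTC response by treatment arm".

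**Analysis.** Section 11.6.2 covers all of these in one sentence: "All binary endpoints in secondary objectives 1-2 and 4-7, will be summarized with point estimates (occurrence rates), and 2-sided Wilson type 95% CIs". For the primary objective, 11.6.1 states "PSA response rates will be compared by treatment arm in a stratified logistic regression model", stratified by race and bone pain. Section 11.6.3 adds frequency tables of toxicity grade. Section 11.6.4 gives a stratified log-rank test for the time-to-event endpoints, including time to SRE. Sections 11.6.6 and 11.6.7 deal with correlative markers.

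**Precision.** Section 11.5.2 seeks at least 25 evaluable AA patients and gives a 95% margin of 0.183 for the rate in that one group. No precision is stated for the AA-versus-Other difference.

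**The concern.** An objective to compare two groups needs an estimate of how they differ, with its uncertainty. The plan provides two rates and two intervals and stops there. Whether the intervals overlap is not a valid substitute, because that check is more conservative than an interval for the difference. Someone who has to report on objective 1 must then judge by eye or choose a contrast, and a set of covariates, after seeing the data.

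Race is also a stratification factor and has its own accrual target, so the omission is not in a peripheral variable. The correlative markers, which the plan labels exploratory, are promised an odds ratio with a CI in 11.6.6; the first secondary objective is promised less. The stakes are moderate: no go/no-go decision depends on this result, but a stated objective has no analysis that answers it.

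**Working it through.** **Step 1: does any clause supply a race contrast?**

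| Section | What it provides | AA-versus-Other contrast? |
|---|---|---|
| 11.6.1 | Logistic comparison of arms, stratified by race and bone pain | No. If the model conditions on strata, race is constant within each stratum and has no coefficient. If race is a covariate, nothing assigns its coefficient to objective 1 |
| 11.6.2 | Rates with Wilson 95% CIs | No |
| 11.6.3 | Grade and IHC frequencies | No |
| 11.6.4 | Kaplan-Meier, stratified log-rank | No (time-to-event only) |
| 11.6.6, 11.6.7 | Odds and hazard ratios for markers | No (markers only) |

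**Step 2: which by-arm binary endpoints share the gap?** Measurable-disease response (2a), toxicity rates (4), crude SRE incidence (5) and CTC response (6) have no between-arm estimate. Time to SRE has the log-rank test. PSA response (2b) is arguably covered, since 11.6.1 speaks of PSA response rates.

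**Step 3: reproduce the plan's own figure.** The Wilson half-width is z/(1+z²/n) × √[p(1−p)/n + z²/(4n²)]. With n = 25, p = 0.5 and z = 1.96 it is 0.1825, which matches the stated 0.183. It is a single-group figure.

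**Step 4: precision of the difference.** Inputs: 82 evaluable patients (11.5.1) and 25 evaluable AA (11.5.2), so Other = 82 − 25 = 57. On the randomised set of 92, 25/0.90 rounds up to 28 AA, leaving 64. Both rates are set at 0.5.

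- Wald half-width: 1.96 × √[0.25 × (1/n₁ + 1/n₂)]. For 25 vs 57 this is 1.96 × √[0.25 × (0.0400 + 0.0175)] = 0.235.
- Newcombe half-width at p = 0.5: the square root of the sum of squared Wilson half-widths. For 25 vs 57 this is √(0.1825² + 0.1256²) = 0.2215.

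| Comparison | Newcombe | Wald |
|---|---|---|
| AA vs Other, 25 vs 57 evaluable | 0.2215 | 0.2351 |
| AA vs Other, 28 vs 64 randomised | 0.2105 | 0.2220 |
| Arm vs arm, 41 vs 41 evaluable | 0.2070 | 0.2164 |

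**Step 5: why two separate intervals are not enough (hypothetical counts only).** AA 12/25 = 0.480, Wilson 0.300 to 0.665. Other 42/57 = 0.737, Wilson 0.610 to 0.834. The intervals overlap between 0.610 and 0.665. The difference is 0.480 − 0.737 = −0.257, and its Newcombe limits are:

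- lower: −0.257 − √[(0.480−0.300)² + (0.834−0.737)²] = −0.461;
- upper: −0.257 + √[(0.665−0.480)² + (0.737−0.610)²] = −0.033.

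The interval for the difference excludes zero although the separate intervals overlap.

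**Step 6: behaviour of an adjusted risk difference.** A logistic model with race, arm and bone pain, standardised to a risk difference with a delta-method CI, was simulated with 2,500 replicates per setting. Arm rates were 0.75 and 0.50 (11.5). Assumed, because the documents do not give them: AA effect of 0, −0.10 or −0.20; bone pain in 30% or 50% of patients, with no effect on outcome.

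- 25 vs 57: mean half-width 0.214 to 0.219, coverage 0.933 to 0.947, odds-ratio limits about 2.8-fold either side.
- 28 vs 64: mean half-width 0.203 to 0.208, coverage 0.928 to 0.952.

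The Monte Carlo standard error is √(0.95 × 0.05/2500) = 0.0044, so the lowest value, 0.928, is about 5 standard errors below 0.95. The delta-method interval runs slightly narrow at these sizes.

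**The case against.** The best defence is that description was intended. Section 11.4.1 calls even the primary comparison non-definitive, and 11.5.2 justifies the 25 AA patients by generalisability and single-group precision, which a Wilson rate serves. Any reader given both rates and denominators can compute a crude difference. This has weight, and it is why the contrast should be for estimation and not a test. It does not remove the mismatch. The screening rationale concerns the primary endpoint. Where the plan limits interpretation to exploration (11.6.6, 11.6.7) it says so, and it says nothing of the kind for objective 1. A crude difference worked out by a reader is also neither pre-stated nor adjusted for arm and bone pain. Rewording the objective as descriptive would restore consistency, but would give up the stated comparison.

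The overlap example is chosen to make the point. With one more AA responder, 13/25 against 42/57, the Newcombe interval is −0.426 to +0.003 and includes zero. The example shows what can happen, not what is likely here.

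Intervals for every toxicity type will include sparse counts. That supports keeping them descriptive, with no multiplicity claims.

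A reader might also infer that the 11.7 timeline is wrong because it leaves out the AA target. The documents do not support that. Section 11.7.2 correctly projects the time to enrol 92 patients (92/42 × 12 = 26.3 months to 92/30 × 12 = 36.8 months). Section 11.5.2 words the AA number as something sought and already foresees closing accrual to non-AA patients.

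**Conclusion.** The concern holds as a specification gap, not an arithmetic error. Objective 1 calls for a comparison that no part of Section 11.6 delivers, and 2a, 4, 5 (crude incidence only) and 6 have the same mismatch by arm. PSA response and time to SRE are not part of it.

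A pre-stated AA-versus-Other difference would carry a 95% half-width of about 0.22 to 0.235 at 25 vs 57. That assumes the AA goal is just met, 82 patients are evaluable and rates are near 0.5. The by-arm differences would have half-widths up to about 0.21 to 0.22 at 41 vs 41, and wider where fewer patients contribute, as for measurable disease.

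A reader might infer that the trial needs a powered race test, or that its main conclusion is at risk. Neither follows: the documents give no race-specific rates, rest no decision on this objective, and specify the primary arm comparison separately. The change should be made because it is cheap and the objective is otherwise unanswered.

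**What to change.** **Objective 1, in 11.6.2.** State that the AA-versus-Other odds ratio with 95% CI will be estimated from a logistic model with race, arm and bone pain, on both analysis sets in 11.6.1. Add a risk difference with 95% CI, by one of:

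- a Newcombe or stratified Newcombe-type interval; or
- a difference standardised from the model, noting that its delta-method CI had simulated coverage of about 0.93 to 0.95 at these sizes.

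Label both as estimation only, quote the expected half-width (about 0.22 to 0.235 for 25 vs 57), and call any arm-by-race term exploratory.

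**Objectives 2a, 4, 5 (crude SRE incidence) and 6.** Add a between-arm risk difference with a Newcombe 95% CI, on the toxicity-evaluable set for toxicity as 11.6.2 already requires. Mark these as descriptive, with no multiplicity claims.

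**Cost.** A few sentences in Section 11.6 and a few more intervals to report, from data already being collected. The number of patients, alpha, the primary comparison and Section 11.7 stay as they are.

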As enzalutamide inhibits the gamma amino butyric acid (GABA)-gated chloride channel, convulsion potential was assessed in single- and multiple-dose studies in mice. Oral therapy daily for 7 days was associated with convulsions in a dose-dependent manner with doses \geq 200 mg/kg being active. When administered as a single dose of 400 mg/kg the treatment was also associated with convulsions. At the highest dose at which no convulsions occurred (single dose, 100 mg/kg), the maximum plasma concentration (Cmax) and area under the curve at 24 hours after dosing (AUC24) were at least 2.5-times higher than those in patients receiving 160 mg/day. The incidence of seizures was noted in 0.6% of the patients treated in the registration trial. 5 of 800 patients experienced seizures on enzalutamide therapy and none on placebo therapy. The seizures were reversible after therapy was discontinued [5]. One case of status epilepticus (confusion associated with partial complex-status epilepticus) required medical intervention; the four other seizures were self-limited and did not recur after study-drug discontinuation. Four of the seizures were witnessed. Potentially predisposing factors were present in several patients. Two patients had brain metastases, 1 of whom had a seizure reported 26 days after the last dose of enzalutamide. One patient had inadvertently been administered lidocaine intravenously immediately before the seizure, and 1 patient with brain atrophy had an unwitnessed event classified as a seizure, in the context of a history of heavy alcohol use, after initiation of haloperidol 7 days beforehand. One additional adverse event reported by the investigator as syncope had several features suggestive of seizure. The enzalutamide group had a lower incidence of adverse events of grade 3 or above (45.3%, vs. 53.1% in the placebo group). The median time to the first such adverse event was 12.6 months in the enzalutamide group, as compared with 4.2 months in the placebo group. There was a higher incidence of all grades of fatigue, diarrhea, hot flashes, musculoskeletal pain, and headache in the enzalutamide group than in the placebo group. Cardiac disorders were noted in 6% of patients receiving enzalutamide and in 8% of patients receiving placebo (with cardiac disorders of grade 3 in 1% and 2%, respectively). Hypertension or increased blood pressure was observed in 6.6% of patients in the enzalutamide group and 3.3% of those in the placebo group.

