5.4 Agent Administration

Starting doses of the agents are as follows:

Enzalutamide is provided as 40 mg soft gelatin capsules in bottles with induction-sealed childresistant caps.

Directions for Administration

Study drug doses should be taken as close as possible to the same time each day. All study patients on enzalutamide will take 4 capsules of study drug once daily unless dose adjustment has been done. Patients randomized to bicalutamide will take 1 tab of 50 mg daily dose. If dosing is missed on one day for any reason, double-dosing should NOT occur the following day. The oral medications can be taken with or without food. Documentation of daily dose will be conducted by patient on a study diary.

Storage and Labeling

Study drug should be stored in a secure location with limited access within the following temperature range: 59°F to 86°F (15°C to 30°C). Bottles will be labeled with the study protocol number, medication or bottle number, contents, directions for use, storage directions. Patients will be instructed to store study drug at room temperature out of the reach of children.

6.0 TOXICITIES TO BE MONITORED AND DOSAGE MODIFICATION:

All toxicities will be graded as per NCI Common Toxicity (CTCAE) version 4.0.

Toxicity evaluation will be done monthly for the first 8 visits starting with day 1 and after that every 3 months until progression. Radiologic evaluation at months 6 and 12 with scans (CT scans and bone scan), and PSA levels every month for the first 8 visits and after that every 3 months. After 12 months radiologic evaluation is required annually while patient is on study.

Dose Reduction/Dose Adjustment

Patients who experience a Grade 3 or greater toxicity that is attributed to study medication, and cannot be ameliorated by the use of adequate medical intervention should have their treatment interrupted until the toxicity improves to a Grade 2 or lower severity. Patients may subsequently be re-started on study drug, including at a reduced dose (80 mg daily of enzalutamide), with the written approval of the PI (or designee). **Any reports of seizure activity for patients randomized to enzalutamide require immediate and permanent discontinuation of this therapy.**

There are no dosage adjustments for hematologic toxicity.

Dosage adjustments for Non-hematologic Toxicity: a.

Diarrhea Toxicity:

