8.4 Duration of stable disease

Stable disease is measured from the start of the treatment until the criteria for progression are met, taking as reference the smallest measurements recorded since the treatment started. Tumor evaluations are recommended every three cycles while on protocol therapy and then as clinically required by the treating physician.

8.5 Time to Treatment Failure:

From date of registration to date of progressive disease, or date patient is taken off study for any reason. All patients, regardless of the number of completed cycles of therapy, will be included for toxicity evaluation. All subjective toxicities encountered during the study will be evaluated according to the NCI toxicity criteria. Objective toxicities will be based upon the greatest severity that occurred at any time during a treatment cycle and not on the severity noted at the beginning of the next cycle.

8.6 Time to Progression:

From date of registration to date of progressive disease, defined as either progression of measurable disease by RECIST 1.1 criteria, or progression of bone metastases or occurrence of new skeletal related event or by PSA per PCWG 2 criteria [Appendix B].

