8.11 Toxicity- Evaluable patients

All patients registered on the protocol and starting therapy will be considered toxicity evaluable. Toxicity will be graded per the CTCAE criteria 4.0.

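### Toxicity is compared by arm as crude proportions while assessment runs until progression, so longer observation on Arm A would modestly inflate its rates

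*Combined protocol and SAP*

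**What the plan says.** Sections 1.0 and 11.2 set secondary objective 4: "To compare the rates of each type of toxicity by treatment arm". Section 11.3.5 makes this a binary outcome per toxicity: "the endpoints will be the occurrence rate of each specific type of toxicity observed". Section 11.6.2 gives the estimator: "All binary endpoints in secondary objectives 1-2 and 4-7, will be summarized with point estimates (occurrence rates), and 2-sided Wilson type 95% CIs". Section 11.6.3 adds one-way tables of grade.

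The denominator takes no account of time on treatment. Section 11.6.2 states: "The analysis of toxicity rates will be performed using only the toxicity-evaluable (t-e) patients". Section 8.11 defines that set: "All patients registered on the protocol and starting therapy will be considered toxicity evaluable". Section 8.5 repeats the idea: "All patients, regardless of the number of completed cycles of therapy, will be included for toxicity evaluation".

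The observation period depends on outcome. Section 6.0 states: "Toxicity evaluation will be done monthly for the first 8 visits starting with day 1 and after that every 3 months until progression". Serious events are reported until 30 days after the last dose (12.5), and study therapy continues past month 7 (5.3).

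Section 11.6.4 reserves Kaplan-Meier and log-rank methods for secondary objectives 3 and 5. Skeletal events therefore get both an incidence and a time-to-event analysis, while toxicity gets only the proportion.

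**The concern.** A proportion of patients with an event has a clear meaning when everyone is watched for the same time. Here the watching stops at progression, and delayed progression is one of the benefits the trial looks for: time to progression, progression-free survival and time to treatment failure are all compared by arm. If Arm A does better on these, its patients contribute more months in which a toxicity can be recorded. Two drugs with identical monthly risk would then show different crude rates, with the more effective one looking more toxic. If Arm A were observed for less time, the distortion would run the other way.

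At stake is how the side-by-side toxicity rates and their intervals are read. Worst-grade tables share the problem, because the worst grade can only rise with longer observation.

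**Working it through.** The documents give no figure for the toxicity comparison, so there is none to reproduce. The study duration matters, and it does reproduce: 92 patients at 42 or 30 per year take 92/42 x 12 = 26.3 or 92/30 x 12 = 36.8 months, stated as 27-37 in 11.7.2. Adding 7 months gives the stated 34-44 (11.7.3).

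**Inputs from the documents.** Accrual of 27 months with cutoff at 34, or accrual of 37 months with cutoff at 44; up to 46 patients per arm (11.5.1); toxicity assessment ending at progression (6.0).

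**Assumptions, not in the documents.** The toxicity hazard h is constant and the same in both arms, giving 20% or 10% risk by 12 months of observation. Time to progression is exponential, with a median of 12 months on Arm B and 15, 18 or 24 on Arm A. Accrual is uniform, and data are cut at the stated study end.

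**Formulas.**
- h = -ln(1 - risk)/12: 0.0186 per month for 20%, 0.00878 for 10%.
- g = ln 2 / median: 0.0578, 0.0462, 0.0385 and 0.0289 for medians of 12, 15, 18 and 24 months.
- For a patient with potential follow-up T: P(event recorded) = h/(h+g) x [1 - exp(-(h+g)T)].
- Average over T uniform from 7 months to the cutoff C, with accrual A = C - 7 and k = h+g: (h/k) x [1 - (exp(-7k) - exp(-Ck))/(kA)].

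**Worked case: 20% risk, 44-month cutoff.**
- Arm B, median 12: k = 0.0764 and h/k = 0.2435. The bracket is 1 - (0.5860 - 0.0347)/(0.0764 x 37) = 0.805, giving 19.6%.
- Arm A, median 24: k = 0.0475 and h/k = 0.3917. The bracket is 1 - (0.7172 - 0.1238)/(0.0475 x 37) = 0.662, giving 25.9%.
- The gap is 6.3 points with no difference in monthly risk. Mean time to progression or cutoff is 12.5 months on B and 17.3 on A.

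**All cases (crude % with event).**

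| 12-month risk | Cutoff | B, median 12 | A, 15 | A, 18 | A, 24 | Gap (points) |
|---|---|---|---|---|---|---|
| 20% | 34 months | 18.3 | 20.1 | 21.4 | 23.3 | 1.8-5.0 |
| 20% | 44 months | 19.6 | 21.8 | 23.5 | 25.9 | 2.2-6.3 |
| 10% | 34 months | 9.3 | 10.3 | 11.0 | 12.1 | 1.0-2.7 |
| 10% | 44 months | 10.1 | 11.3 | 12.3 | 13.7 | 1.2-3.5 |
| 20% | none | 24.4 | 28.7 | 32.6 | 39.2 | 4.3-14.8 |
| 10% | none | 13.2 | 16.0 | 18.6 | 23.3 | 2.8-10.1 |

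The last two rows are the limit h/(h+g), which needs unlimited follow-up. With equal medians the gap is zero in every row.

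**Effect of the remedy.** Restricting the same crude proportion to 7 months (T = 7) gives 10.1% on B against 10.5-11.1% on A at the higher hazard, and 4.9% against 5.1-5.4% at the lower. The residual gap is 0.2-1.0 points, from patients who progress before month 7. The rate per patient-month equals h in both arms, so that gap is zero under a constant hazard.

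**The case against.** Several points on the other side stand.

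- **The analysis is descriptive.** Objective 4 says compare, but 11.6 names no between-arm toxicity test, so no planned p-value or error rate is distorted. Proportions over all treated patients are a legitimate safety summary. The objective still invites readers to set the two columns side by side, so the unequal observation time needs handling.
- **The gap is small against the precision.** With 46 per arm, the Wilson 95% interval around 9/46 (20%) runs from about 11% to 33%. A drift of 1-6 points lies well inside it, but it has a predictable direction and is easy to avoid.
- **Ever-occurred is an inference.** The plan does not use that phrase. It follows from a binomial interval on an occurrence rate over everyone who started therapy.
- **Treatment time need not track progression.** Sections 5.3 and 9.0 give different conditions for stopping study drug, one combining progression or a skeletal event with a further event and the other listing progression alone. They need to be reconciled. The argument relies on Section 6.0, which ends toxicity assessment at progression.

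Two stronger readings are tempting. A reader might infer that the safety side of the decision to plan a larger study would rest on an artefact. Section 11.4.1 ties that decision to an efficacy signal in the primary endpoint and states no toxicity criterion. A reader might also cite the Section 2.0 account of the earlier placebo-controlled trial, where median time to first grade 3 or higher event "was 12.6 months in the enzalutamide group, as compared with 4.2 months in the placebo group". That shows that timing adds information. It is no example of the bias, because crude incidence was also lower on enzalutamide (45.3% against 53.1%).

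**Conclusion.** The point holds as a modest weakness of the toxicity comparison. Objective 4 calls for a comparison by arm, the only estimator is a crude proportion, and assessment ends at an event that the treatment may delay. The direction of the distortion follows whenever Arm A is observed longer at equal monthly risk.

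The size is about 1-6 points within the stated 34-44 months, under assumed equal constant hazards (10-20% by 12 months) and assumed medians of 12 months against 15-24. A reader might infer a bias of up to 15 points, but that needs follow-up well beyond the stated duration. Because therapy may continue after month 7, a later data cut would move towards it: at 60 months after 37 months of accrual, the 20% case with medians 12 and 24 gives 23.0% against 33.0%. For events that occur mainly in the first months the gap is near zero.

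The primary endpoint and the sample size are unaffected.

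**What to change.** In 11.6.2 and 11.6.3:

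1. Base the between-arm toxicity comparison on incidence within the first 7 months from the start of randomised drug. First occurrence by visit is enough, so exact onset dates, whose collection the documents do not state, are not needed. The clock should start at randomised drug because Sections 5.3 and 7.0 backdate the treatment start of late-induction patients to their earlier hormone therapy. State how many patients per arm were observed for the whole window.
2. Add, as a supplement, incidence per 100 patient-months on randomised drug. Section 5.4 already has patients record daily doses in a diary.
3. Keep the crude whole-study rates and grade tables, labelled as descriptive and not adjusted for observation time.

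The cost is SAP wording and two extra table columns, with no new patients or visits. There are limits. The person-time rate assumes a roughly constant hazard and can mislead for early-onset effects. After month 7, onset may be known only to the 3-monthly visit interval; for late-induction patients, whose visits are shifted by prior hormone therapy, part of the 7-month window can fall in that phase. Randomisation should balance this between arms.
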